9.2.3.2 Visit 1; Baseline Visit

Upon patient enrolment, the following will be recorded on the patient's eCRF.

- Visit date
- Diagnosis: date of the diagnosis of T2DM, Family history of T2DM
- Inclusion / Exclusion criteria
- Data release consent form: Date of data release consent form

Boehringer-Ingelheim**Non-interventional Study Protocol****BI Study Number 1275-0028****c37168579-01**

Proprietary confidential information © 2022 Boehringer Ingelheim International GmbH or one or more of its affiliated companies

- Demographic data: Year of birth(age), Gender, Pregnancy, Previous allergy, Height, Smoking status
- Diabetes mellitus related complication(Retinopathy, Neuropathy, Nephropathy, Vasculopathy, Others)
- Medical history: Renal impairment, Hepatic impairment, Others. (history of concomitant disease within 6 months prior to baseline)
- Physical examination: Body weight, Blood pressure (SBP, DBP)
- Renal function test: Serum creatinine, eGFR, Urine ACR if blood test result is available(the most recent data prior to baseline)
- Effectiveness assessment: HbA1c, FPG (within 1 month prior to baseline)
- Concomitant anti-hyperglycemic agent: record any anti-hyperglycemic agents that have been taken at least once (within 1 month prior to baseline)
- Concomitant medications: record all medications that have been taken at least once (within 1 month prior to baseline)
- Dose of Esgliteo given (Daily dose, Start date)

At visit 1, the patient will be requested to contact the treating physician in the event of any adverse events noted after initiating Esgliteo treatment.

9.2.3.3 Visit 2; 12 weeks from Visit 1

After 12 weeks from Visit 1, the patients will return for follow-up. The followings will be noted and recorded in the eCRF.

- Visit date
- Physical examination: Body weight, Blood pressure (SBP, DBP)
- Any changes of Esgliteo given
- Effectiveness assessment: HbA1c, FPG (Within 1month prior to Visit 2)
- Renal function test: Serum creatinine, eGFR, Urine ACR if blood test result is available (The most recent data since last visit, except previously entered data)
- Concomitant anti-hyperglycemic agent including new medications taken since last visit: any changes in the concomitant medications (dose and dosing intervals)
- Concomitant medications including new medications taken since last visit: any changes in the concomitant medications (dose and dosing intervals)

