9.2.5 Flow Chart

Data points	Baseline	Follow-up 1	Follow-up 2
Visit Number	1	2	3
Week/s	0	12	24
Informed consent	X		
Diagnosis	X		
Inclusion / exclusion criteria	X		
Demographics	X		
Family history of T2DM	X		
Diabetes mellitus complications	X		
Medical history	X		
Physical examination	X	X	X
Anti-diabetic agents	X	X	X
Concomitant medications	X	X	X
Esgeliteo administration status	X	X	X
Renal function	X ^A	X ^A	X ^A
Effectiveness endpoints	X	X	X
Overall effectiveness evaluation			X
Changes in lab tests		X ^A	X ^A
Adverse events		X	X
Study completion		X	X

^A: If applicable

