9.3.3 Assessment Criteria

9.3.3.1 Assessment of safety

- Adverse events (event name/ symptoms/ sign/ identify hypoglycemia symptoms)
- Onset date, End date
- Intensity (Mild/ Moderate/ Severe)
- Serious (Serious/ Non-Serious)
- Outcome of the event (Recovered/ Not yet recovered/ Sequela/ Fatal/ Unknown)
- Causality (Certain/ Probable/Likely/ Possible/ Unlikely/ Conditional/ Unclassified/ Unassessable/Unclassifiable)
- Action taken with study drug due to AE (Dose not changed/ Dose reduced/ Dose increased/ Drug withdrawn/ Not applicable)
- Adverse Event of Special interest (Hepatic injury/ Decreased renal function/ Metabolic acidosis, ketoacidosis and diabetic ketoacidosis (DKA)/ Lower limb amputation)

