The term Adverse Event of Special Interest (AESI) relates to any specific AE that has been identified at the project level as being of particular concern for prospective safety monitoring and safety assessment within this study, e.g. the potential for AEs based on knowledge from other compounds in the same class. AESIs need to be reported to the [REDACTED] within the same timeframe that applies to SAEs.

The following are considered as AESIs:

- Hepatic injury
 - An elevation of AST and/or ALT \geq 3-fold ULN combined with an elevation of total bilirubin \geq 2-fold ULN measured at the same visit, or in samples drawn within 30 days of each other, OR
 - An elevation of AST and/or ALT \geq 3-fold ULN and INR \geq 1.5-fold ULN measured at the same visit, or in samples drawn within 30 days of each other, OR
 - An elevation of AST and/or ALT \geq 3-fold ULN with new onset, or worsening of fatigue, nausea, vomiting, right upper quadrant pain or tenderness, fever, rash, and/or eosinophilia ($>5\%$), OR
 - An isolated elevation of AST and/or ALT \geq 5-fold ULN
- Decreased renal function
 - Creatinine value shows a >2 -fold increase from baseline and is above the ULN
- Metabolic acidosis, ketoacidosis and diabetic ketoacidosis (DKA)
- Lower limb amputation
 - Amputation (i.e. resection of a limb through a bone)
 - Disarticulation (i.e. resection of a limb through a joint)
 - Auto-amputations (i.e. spontaneous separation of non-viable portion of the lower limb)

Not included in this definition are debridement (removal of callus or dead tissue), procedures on a stump (like stump revision, drainage of an abscess, wound revision etc.) and other procedures (e.g., nail resection or removal) without a concomitant resection of a limb (amputation or disarticulation).

Each lower limb amputation, disarticulation, or auto-amputation should be reported separately. The SAE report should include the date of the procedure, the level of amputation or disarticulation, the medical condition(s) leading to the procedure and if the patient had some of the known risk factor(s) for lower limb amputation.

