11.2 ADVERSE EVENT AND SERIOUS ADVERSE EVENT COLLECTION AND REPORTING

The investigator shall maintain and keep detailed records of all AEs in their patient files.

Collection of AEs

The study is a non-interventional study in real-world situation and will be conducted within the conditions of the approved marketing authorization. For this reason, the following AE collection and reporting requirements have been defined.

All adverse events occurred from the signing date on data release consent form to last visit date of monitoring period need to be collected, documented and reported to the sponsor using the AE page of eCRF(14.1).

The investigator carefully assesses whether an AE constitutes an ADR using the information below.

Causal relationship of adverse event

The definition of an adverse reaction implies at least a reasonable possibility of a causal relationship between a suspected medicinal product and an adverse event. An adverse reaction, in contrast to an adverse event, is characterized by the fact that a causal relationship between a medicinal product and an occurrence is suspected.

Medical judgment should be used to determine the relationship, considering all relevant factors, including pattern of reaction, temporal relationship, de-challenge or re-challenge, confounding factors such as concomitant medication, concomitant diseases and relevant history.

Arguments that may suggest a **reasonable causal relationship** could be:

- The event is **consistent with the known pharmacology** of the drug
- The event is known to be caused by or **attributed to the drug class**
- A **plausible time to onset of the event** relative to the time of drug exposure
- Evidence that the **event is reproducible** when the drug is re-introduced
- **No medically sound alternative etiologies** that could explain the event (e.g. preexisting or concomitant diseases, or co-medications).
- The event is typically **drug-related and infrequent in the general population** not exposed to drugs (e.g. Stevens-Johnson syndrome).
- An indication of dose-response (i.e. greater effect size if the dose is increased, smaller effect size if dose is diminished).

Arguments that may suggest that there is **no reasonable possibility of a causal relationship** could be:

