8. SAFETY ANALYSIS

Safety analyses will be performed on Safety set.

An adverse event (AE) is defined as any untoward medical occurrence in a patient or clinical investigation subject administered a medicinal product and which does not necessarily have a causal relationship with this treatment. An adverse event can therefore be any unfavorable and unintended sign (e.g. an abnormal laboratory finding), symptom, or disease temporally

CONFIDENTIAL

STATISTICAL ANALYSIS PLAN

associated with the use of a medicinal product, whether or not considered related to the medicinal product.

An adverse drug reaction (ADR) is defined as a response to a medicinal product which is noxious and unintended. Response in this context means that a causal relationship between a medicinal product and an adverse event is at least a reasonable possibility. Adverse reactions may arise from use of the product within or outside the terms of the marketing authorization or from occupational exposure. Conditions of use outside the marketing authorization include off-label use, overdose, misuse, abuse and medication errors.

ADR is defined as the case where the causal relationship with Esglito evaluated by the investigator falls under the following.

- Certain
- Probable/Likely
- Possible
- Conditional/Unclassified
- Unassessable/Unclassifiable

The following Aes are defined as serious adverse event (SAE).

- Results in death
- Is life-threatening
- Requires in-patient hospitalization or prolongation of existing hospitalization
- Results in persistent or significant disability or incapacity
- Is a congenital anomaly/birth defect
- Other medical criteria

Unexpected adverse event (UAE) means any adverse event not listed in the permit.

Adverse events of special interest (AESI) refer to any of the following cases.

CONFIDENTIAL

STATISTICAL ANALYSIS PLAN

- Hepatic injury
 - An elevation of AST and/or ALT >3-fold ULN combined with an elevation of total bilirubin >2-fold ULN measured in the same blood draw sample.
 - An isolated elevation of AST and/or ALT >5-fold ULN (without an elevation of total bilirubin >2-fold ULN)
- Decreased renal function
 - Creatinine value shows a >2-fold increase from baseline and is above the ULN
- Metabolic acidosis, ketoacidosis and diabetic ketoacidosis (DKA)
- Lower limb amputation
 - Amputation (i.e. resection of a limb through a bone)
 - Disarticulation (i.e. resection of a limb through a joint)

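### Renal tests are recorded at all three visits when a result exists, but no planned output summarises them or applies the creatinine rule that defines the special-interest event of decreased renal function.

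*Protocol*

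**What the plan says.** **Collection.** Protocol 9.2.3.2 (Visit 1) lists "Renal function test: Serum creatinine, eGFR, Urine ACR if blood test result is available", taking the latest result before baseline. Protocol 9.2.3.3 (Visit 2) and 9.2.3.4 (Visit 3) list the same three tests, "if blood test result is available (The most recent data since last visit, except previously entered data". The flow chart (9.2.5) marks renal function at weeks 0, 12 and 24 with the footnote "A: If applicable".

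**Definition.** Protocol 11.1 defines the AESI of decreased renal function by "Creatinine value shows a >2 -fold increase from baseline and is above the ULN". SAP 8 repeats it: "Creatinine value shows a >2-fold increase from baseline and is above the ULN".

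**Capture.** Protocol 9.3.3.1 makes the AESI category one item of the adverse event assessment: "Adverse Event of Special interest (Hepatic injury/ Decreased renal function/ Metabolic acidosis, ketoacidosis and diabetic ketoacidosis (DKA)/ Lower limb amputation". Under Protocol 11.2, adverse events "need to be collected, documented and reported to the sponsor using the AE page of eCRF(14.1".

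**Analysis.** Protocol 9.3.2.1 presents safety endpoints as adverse event frequencies, with AESI among them, and 9.7.2 plans no laboratory summary. SAP 8.1 to 8.7 summarise adverse events only. Renal impairment enters the SAP analyses as a Yes/No factor (for example in 7.3.3 and 8.3.1) with no criterion attached.

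**The concern.** Safety is the primary objective, and decreased renal function is one of four AESI categories. Its definition is a calculation on two creatinine values and a reference limit. The study records creatinine before and during treatment wherever a result exists, but the plan never runs that calculation on those values. The count in the report will be the number of events that investigators entered as adverse events and flagged as this AESI.

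Two things are at stake. First, a recorded doubling that was not filed as an event would be left out of the count. Second, no planned table gives the number of patients with a baseline and a follow-up creatinine. A reader who sees zero renal AESIs could not tell whether that means none among most of the cohort or none among a tested minority.

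**Working it through.** There is no figure in the plan to reproduce: the 600 patients are a regulatory requirement, with no formula behind them. The main check is a reading of the plan.

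**Step 1. Where the renal tests appear in the SAP.**
- Creatinine: only in the AESI definition (SAP 8).
- eGFR: only in the exclusion criteria (SAP 3.3). It can act indirectly through the safety-set exclusion for eligibility violations (SAP 4.2, item h), but that is not an analysis of renal function.
- Urine ACR: nowhere.
- Table 3 (derived variables): a generic change-from-baseline row, but no renal variable and no derivation of the creatinine rule.
- Table 7 (A1 to D16): no laboratory table.
- SAP 11 (changes to planned analysis): one item, on average daily dose; nothing on renal tests.

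**Step 2. What feeds the AESI tables.** C1 and C6 (safety set) and C24 and C29 (long-term safety set) count adverse events of the AESI type. The summaries for special populations and off-label use (C20, C22) do the same. No output takes creatinine values as input. A value in the renal-function item with no matching adverse event entry therefore cannot reach any of these tables.

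**Step 3. Whether the rule can be applied to the recorded data.**
- Baseline value: the most recent before baseline, with no age limit. HbA1c and FPG, by contrast, must be within one month.
- Follow-up value: the most recent since the last visit, so not strictly a week-12 or week-24 value. A transient peak followed by a normal result could still be missed.
- ULN: not among the items listed for any visit. The eCRF itself is not in the documents, so whether a ULN was recorded is unknown.

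The more-than-two-fold part can be applied to patients with both values. The ULN part may not be possible.

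**Step 4. What a zero count would mean.** The exact two-sided 95% upper limit for 0 events in n patients is 1 − 0.025^(1/n).
- n = 600 (all tested): 1 − 0.025^(1/600) = 0.61%.
- n = 300 (assumed): 1 − 0.025^(1/300) = 1.22%.

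Halving the number tested doubles the limit, and the planned tables would not show which n applies.

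**Step 5. Effect of incomplete filing (illustration; rates and shares are assumed).** With true rate p and share s of cases filed as AESIs, the chance that at least one of 600 patients is counted is 1 − (1 − ps)^600.

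| True rate p | All filed (s = 1) | Half filed (s = 0.5) |
|---|---|---|
| 0.25% | 77.7% | 52.8% |
| 0.5% | 95.1% | 77.7% |
| 1% | 99.8% | 95.1% |

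Incomplete filing matters most when the event is rare. The documents give neither p nor s, so this shows sensitivity and is not an estimate.

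**The case against.** **The SAP follows the protocol.** This stands. Protocol 9.3.2.1 and 9.7.2 plan adverse event frequencies and no laboratory analysis, so a reader who infers that the SAP dropped a planned analysis would be wrong. The gap is in both documents. But AESI is a listed safety endpoint, and applying its written definition to recorded values adds no new endpoint.

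**Investigators are prompted.** Also true. Visits 2 and 3 have an AESI item and a separate item for clinically significant laboratory changes from pre-treatment data. An abnormal laboratory finding can be an adverse event (Protocol 11.1), and AESIs must be reported within 24 hours (11.2). A reader might infer that the AESI rests on unaided investigator reporting; the documents do not support that. A missed case requires an investigator to enter the value and not report the event. What remains is that the documents describe no reconciliation of laboratory values with AESIs. The automatic checks in Protocol 9.8 cover plausibility, consistency and completeness. The data management plan may contain more, but it is not among the documents.

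**Testing is conditional.** A reader might take the data as complete for 600 patients at three visits. They are not: every visit carries the availability condition. This limits what a table can show and is the reason to report the number tested.

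**It may be too late to query.** The SAP's signature certificate is dated 19 April 2023, after the planned end of data collection on 30 November 2022. Under SAP 6.5, errors listed after database lock are not reflected in the analysis. This affects how mismatches are handled, but a listing remains possible.

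**Conclusion.** The point holds as a cheap improvement. The plan records creatinine, eGFR and ACR where available, defines a special-interest event by a creatinine rule, and then neither summarises the tests nor applies the rule to them. A recorded doubling that was not filed as an adverse event would not be counted, and the number of patients assessed would not be visible.

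Its size cannot be stated as a number of missed events, because the documents give no event rate, filing rate or testing rate. It is tempting to say that each missed case is 1/600 = 0.17%, or that a zero count bounds the risk at 0.61%. Both assume that all 600 patients are in the safety set and were tested. SAP 4.2 lists eight exclusions from that set and testing is conditional, so neither figure is a finding about this study.

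A reader might also infer that the SAP defines renal impairment by medical history. It gives no definition. Protocol 9.2.3.2 records renal impairment under medical history, which makes that the likely source, but the SAP does not say so, nor does it use baseline eGFR to describe the group.

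The conclusion rests on the protocol and SAP alone; a check in the data management plan or the eCRF could narrow the gap.

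**What to change.** Add to SAP 8:

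1. A descriptive table of creatinine, eGFR and urine ACR at baseline, at each follow-up and at last value, with the number tested and the change from baseline. Add a baseline-to-last shift table by eGFR class, with class limits stated in advance.
2. A listing and count of patients whose recorded creatinine meets the documents' own rule. The denominator is patients with both a baseline and a follow-up value. Set the result beside C6 and C29.

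State the units, the source of the ULN and the age of the baseline value. If no ULN was recorded, list the more-than-two-fold rises and say that the ULN part could not be applied. State where the Yes/No for renal impairment comes from. If the database is still open, query mismatches between the listing and the reported AESIs; if not, report them as a listing.

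**Cost.** Two tables and a listing from data already collected, with no patient contact, plus some work to settle the ULN and the baseline dates. The downside is interpretation: testing is selective, the baseline has no time window, and follow-up values are not tied to a fixed week. The outputs should be labelled descriptive, with no tests.

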9.2.3.5 End of study and follow-up period

Patients with adverse events noted at the final follow-up visit or upon premature discontinuation of Esgliteo will be monitored further until the study completion. Alternatively, those patients will be followed up until the NIS physician and sponsor agree that no further follow-up is necessary.

9.2.4 Study Discontinuation

Boehringer Ingelheim reserves the right to discontinue the study overall or at a particular study site at any time for the following reasons:

1. Failure to meet expected enrolment goals overall or at a particular study site

2. Emergence of any effectiveness/safety information that could significantly affect continuation of the study
3. Violation of Good Pharmacoepidemiology Practice (GPP), the study protocol, or the contract by a study site, investigator or research collaborator, disturbing the appropriate conduct of the study

The investigator/the study site/research collaborator will be reimbursed for reasonable expenses incurred in case of study/site termination (except in case of the third reason).

9.2.5 Flow Chart

Data points	Baseline	Follow-up 1	Follow-up 2
Visit Number	1	2	3
Week/s	0	12	24
Informed consent	X		
Diagnosis	X		
Inclusion / exclusion criteria	X		
Demographics	X		
Family history of T2DM	X		
Diabetes mellitus complications	X		
Medical history	X		
Physical examination	X	X	X
Anti-diabetic agents	X	X	X
Concomitant medications	X	X	X
Esgeliteo administration status	X	X	X
Renal function	X ^A	X ^A	X ^A
Effectiveness endpoints	X	X	X
Overall effectiveness evaluation			X
Changes in lab tests		X ^A	X ^A
Adverse events		X	X
Study completion		X	X

^A: If applicable

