- Any changes in laboratory tests if there is any lab result which was clinically significant compared to data before Esgliteo therapy (This data is collected on the basis of medical need, i.e. independent of the NIS)
- Any adverse events noted, AESI (Adverse Event of Special interest)
- Study completion status (if necessary)

- The final effectiveness evaluation(if necessary)
- NIS physician's electronic signature for data integrity (if necessary)

9.2.3.4 Visit 3; 24 weeks from Visit 1

After 24 weeks from Visit 1, the patients will return for follow-up. The followings will be noted and recorded in the eCRF.

- Visit date
- Physical examination: body weight, blood pressure(SBP, DBP)
- Any changes of Esgliteo given
- Effectiveness endpoints: HbA1c, FPG (Within 1month prior to Visit 3)
- Renal function test: Serum creatinine, eGFR, Urine ACR if blood test result is available (The most recent data since last visit, except previously entered data)
- Concomitant anti-hyperglycemic agent including new medications taken since last visit: any changes in the concomitant medications (dose and dosing intervals)
- Concomitant medications including new medications taken since last visit: any changes in the concomitant medications (dose and dosing intervals)
- Any changes in laboratory tests if there is any lab result which was clinically significant compared to data before Esgliteo therapy (This data is collected on the basis of medical need, i.e. independent of the NIS)
- Any adverse events noted, AESI (Adverse Event of Special interest)
- Study completion status(if necessary)
- The final effectiveness evaluation
- NIS physician's electronic signature for data integrity

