9.3.1.4 Number of cases subject to effectiveness evaluation

These cases include those who signed the data release consent form to participate in this study as subject, visited as per the study schedule, took Esglito, and were evaluated for the effectiveness.

Reflecting Ministry of Food & Drug Safety (MFDS) guideline, the cases below shall be excluded from effectiveness analysis (defined below) set in the following order:

- a. Patients excluded from safety analysis set listed in section 9.3.1.3
- b. Patients with missing information of assessment of effectiveness set listed in section 9.3.2.2 at visit 2, visit 3

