9.3.2.2.3 The final effectiveness evaluation

Records by performing the final effectiveness evaluation at the end of the last visit

- ① Improved: If determined as there is any effect of maintaining or improving disease related factors.
- ② Unchanged: If disease related factors have not been changed compared with before administration, and not determined as there is any effect of maintaining symptoms.
- ③ Aggravated: If disease related factors are worse than before administration.

④ Unassessable: If it cannot be determined due to insufficient information collected.
 (Even though there are any objective indicators present, it is possible to belong to this grade.)

‘Improved’ is assessed as “Effective”, ‘Unchanged’ and ‘Aggravated’ are assessed as “Invalid”.

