9.3.3.2 Assessment of effectiveness

- ① HbA1c(%):
 HbA1c should be collected within 1 month prior to baseline and after 12 weeks, 24 weeks of treatment.
- ② Fasting Plasma Glucose (FPG)(mg/dL):
 FPG should be collected within 1 month prior to baseline and after 12 weeks, 24 weeks of treatment.
- ③ Body Weight(kg):
 Body weight should be collected within 1 month prior to baseline and after 12 weeks, 24 weeks of treatment.
- ④ Blood Pressure (SBP, DBP)(mmHg):
 Blood pressure(SBP, DBP) should be collected within 1 month prior to baseline and after 12 weeks, 24 weeks of treatment.
- ⑤ Final effectiveness evaluation: Final effectiveness evaluation should be accessed and recorded at the end of the last visit.

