4.3 EFFECTIVENESS SET

These cases include those who signed the data release consent form to participate in this study as subject, visited as per the study schedule, took Esgliteo once at least, and were evaluated for the effectiveness.

Reflecting MFDS's guideline, the cases below shall be excluded from effectiveness analysis (defined below) set in the following order.

- a. Cases excluded from safety set
- b. Cases with missing information of effectiveness assessment
- c. Cases omitted in final effectiveness evaluation
- d. Cases whose final effectiveness evaluation was found to be 'Unassessable'

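### The flow chart schedules the final effectiveness evaluation at Visit 3 only, although it is due at each patient's last visit; patients who end at Visit 2 may go unrated, and SAP 4.3(c) would then drop them from every effectiveness analysis

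*Protocol*

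**What the plan says.** Timing of the final evaluation:

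- Protocol 9.3.2.2.3 defines it by the last visit: "Records by performing the final effectiveness evaluation at the end of the last visit". Protocol 9.3.3.2 repeats the rule: "Final effectiveness evaluation should be accessed and recorded at the end of the last visit". SAP 9.3 uses the same timing.
- The flow chart (protocol 9.2.5) marks "Overall effectiveness evaluation" under Visit 3 and leaves Visit 2 blank. The same chart marks study completion under both Visit 2 and Visit 3.
- The Visit 2 list (protocol 9.2.3.3) contains "The final effectiveness evaluation(if necessary"), next to "Study completion status (if necessary"). Neither entry says when it becomes necessary. At Visit 3 (9.2.3.4) the evaluation is unconditional.

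Who is analysed:

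- Protocol 9.3.1.4(b) excludes "Patients with missing information of assessment of effectiveness set listed in section 9.3.2.2 at visit 2, visit 3".
- SAP 4.3(c) excludes "Cases omitted in final effectiveness evaluation" and 4.3(d) excludes "Cases whose final effectiveness evaluation was found to be 'Unassessable'". SAP 4.5(c) and (d) do the same for the long-term effectiveness set.
- SAP 9 runs all efficacy analyses on the effectiveness set, and SAP 6.1 uses observed cases without replacement.

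**The concern.** The rule says last visit, but the schedule that sites are likely to work from says Visit 3. The two agree only for patients who reach Visit 3. Protocol 9.2 foresees follow-up at 12 and/or 24 weeks, and the flow chart provides for completion at Visit 2, so the plan expects some patients for whom they differ.

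Two results are at stake. The first is the effectiveness rate with its exact 95% interval (protocol 9.7.3 item 4, SAP 9.3) and the factor analyses built on it (SAP 9.4 and 9.5). The second is less obvious. SAP 4.3(c) acts on the whole analysis set, so a missing global rating also removes the patient's measured values, including HbA1c, the primary effectiveness endpoint. Reasons for early interruption listed in SAP 9.2 include a change to another antidiabetic, adverse events and refusal to continue. Patients leaving for such reasons could plausibly be rated improved less often than those who stay.

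**Working it through.** **1. Is the blank cell at Visit 2 shorthand for a conditional item?** The flow chart has its own conditional mark, a superscript explained as if applicable, and uses it at Visit 2 for renal function and for changes in laboratory tests. The evaluation carries no mark there. Read literally, the chart does not ask for it at Visit 2.

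**2. Follow one patient through the plan.** Take a patient who attends Visit 2 inside the SAP 6.4 window (day 84 to before day 168), has baseline and week-12 HbA1c, and ends the study there.

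- Under protocol 9.3.2.2.3 and 9.3.3.2, this patient is rated at Visit 2.
- Under the flow chart alone, this patient is not rated.
- If not rated, SAP 4.3(c) removes the patient from the effectiveness set.
- The week-12 HbA1c, FPG, weight and blood pressure changes (SAP 9.1 and 9.2 item 3), the two HbA1c response rates at week 12 (SAP 9.2 items 1 and 2) and the latest-value HbA1c comparison (SAP 9.2 item 4) all lose valid data. The week-24 summaries are unaffected, because the patient has no week-24 value.
- SAP 9.2 item 4 compares HbA1c change across reasons for early interruption. That comparison needs early leavers in the set, so 4.3(c) works against it.

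**3. Size of the effect on the effectiveness rate.** The documents state no effectiveness rate, dropout rate or precision target, and N = 600 is a regulatory requirement, so there is no planned figure to reproduce. With w the share of patients omitted, p the rate among rated patients and r the rate the omitted patients would have had:

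overstatement = p − [(1 − w)p + wr] = w(p − r)

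Illustration, all inputs assumed: w = 0.10 of 600 (60 omitted, 540 rated) and p = 0.80, so 432/540 = 80.0% (exact 95% CI 76.4 to 83.3).

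| r among the 60 omitted | Rate over all 600 | Overstatement |
|---|---|---|
| 80% (48) | 480/600 = 80.0% | 0.10 × 0.00 = 0 points |
| 50% (30) | 462/600 = 77.0% | 0.10 × 0.30 = 3.0 points |
| 30% (18) | 450/600 = 75.0% | 0.10 × 0.50 = 5.0 points |
| 0% (0) | 432/600 = 72.0% | 0.10 × 0.80 = 8.0 points |

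The half-width of the interval is (83.3 − 76.4)/2, about 3.5 points, so the bias could be anything from nothing to more than the reported uncertainty. Over wider assumptions (w from 5% to 30%, p from 70% to 90%, r from 0 up to p) the overstatement runs from 0 to 0.30 × 0.90 = 27 points (378/420 = 90.0% against 378/600 = 63.0%). If omitted patients did better than rated ones, the sign would reverse.

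Here w covers everyone without a rating. The flow-chart conflict can account only for those who end at Visit 2, so the share due to it is smaller than w by an unknown amount.

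**The case against.** The governing rule is clear, and a careful site would follow it. In the Visit 2 list the evaluation stands with the completion status and the physician's signature, all conditional, and the same items close the Visit 3 list. The natural reading is that they apply when Visit 2 is the last visit. The eCRF is not among the documents, and protocol 9.8 describes automatic completeness checks that might catch a missing rating. This stands: the loss is a risk, not a certainty.

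A reader might infer several stronger points that the documents do not support.

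- *That SAP 4.3(c) is an undeclared departure from the protocol.* Protocol 9.3.1.4(b) covers the assessments in section 9.3.2.2, which includes the final evaluation as 9.3.2.2.3. The SAP largely spells out what the protocol implies, so the silence of SAP 11 is not a fault here.
- *That narrowing SAP 4.3(c) would correct the effectiveness rate.* It would not. Under observed-case analysis an unrated patient cannot count as effective or ineffective. The narrowing protects the measured endpoints only; the rate is helped only by obtaining the rating.
- *That patients leaving before Visit 2 would be recovered.* Those without follow-up information are outside the safety set, and so the effectiveness set, whatever the chart says. Many others would have no post-baseline HbA1c or FPG and might be rated unassessable, which SAP 4.3(d) removes.

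Some transparency already exists. SAP 10.1 reports exclusions with reasons, protocol 9.7.2 and 9.9.1 characterise patients lost to follow-up, and SAP 7.4 tabulates reasons for early interruption. Only the split by last visit would be new. Effectiveness is also a secondary objective, and the protocol abstract calls the analyses descriptive.

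**Conclusion.** The conflict is in current text and should be reconciled. Sites may leave patients who end at Visit 2 unrated, and SAP 4.3(c) would then remove them from all effectiveness analyses, including week-12 HbA1c where valid values exist.

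It would go too far to say that the effectiveness rate is inflated. The documents fix neither the number of such patients nor how they would have been rated. The overstatement is w(p − r), which is zero if omitted patients respond as the others do. An upward bias is plausible if they leave for lack of effect or adverse events; the 0 to 8 points at 10% omitted and 80% effective are an illustration on assumed inputs. The effect on the long-term effectiveness set should be small, since membership already requires 24 weeks of treatment and follow-up.

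**What to change.** 1. In the flow chart, mark the overall effectiveness evaluation at Visit 2 as well as Visit 3, with a footnote that at Visit 2 it applies if this is the patient's last visit. In protocol 9.2.3.3, put the same condition in place of the undefined one.
2. Apply SAP 4.3(c) and 4.5(c) only to the final-evaluation tables (D6 to D10 and D16). Patients with a baseline and a post-baseline HbA1c then stay in the HbA1c and other measured endpoints. State at the same time whether SAP 4.3(b) requires values at one follow-up visit or both, because protocol 9.3.1.4(b) leaves this open and the stricter reading would remove the same patients. Check the change against the MFDS guideline that the SAP cites, which is not among the documents.
3. Report the number of unrated patients by last visit attended, alongside the exclusions in SAP 10.1.

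No extra visit or test is needed. The cost is minor wording and analysis work, denominators that differ between tables, and possibly a slightly less favourable rate. Protocol version 5.0 is dated 28 Oct 2022 and data collection was planned to end on 30 Nov 2022, so item 1 may reach few remaining visits. Items 2 and 3 depend only on the analysis. None of this recovers patients with no follow-up before Visit 2.
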